3.6 Exploratory endpoints

To design a profile of the patient-selective sensory phenotypes (using Neuropathic Pain Symptom Inventory (NPSI)) suitable for both topical treatment options. It is our special interest here to investigate the presence of mechanical allodynia in these patients and study the impact of the active treatment options on this sensory abnormality.

4 TRIAL DESIGN

A multicenter three arm, 1:1:1 randomised, open-label comparative trial evaluating topical treatment options versus oral systemic treatment in adult patients suffering from localized neuropathic pain (LNP) syndromes. A wide variety of peripheral neuropathic pain syndromes will be included such as (but not limited to) post-herpetic neuralgia (PHN), post-surgical NP/post-traumatic NP/scar pain, post-amputation NP, post-radiation therapy NP, complex regional pain syndrome (CRPS) type 1.

591 adult patients suffering from LNP will be **randomised 1:1:1** to receive pregabalin, lidocaine 5% medicated plaster or capsaicin 8% patch. Stratification according to positive sensory phenomena such as hyperalgesia and allodynia, spontaneous positive sensory phenomena (such as dysesthesia) and duration of pain will be applied to keep the treatment arms balanced per stratum variable. The Neuropathic Pain Symptom Inventory (NPSI) will be used for this matter. Its factorial structure makes it suitable to capture different aspects of neuropathic pain (NP). The NPSI has been used in several doubleblind trials as a secondary outcome measure, with some dimensions being differentially sensitive to treatment effects.

Stratified randomisation by site and NPSI will be applied, and coordinated centrally which randomizes eligible patients to one of three treatment arms. All investigational medicinal products will be dispensed by the hospital pharmacies of the individual participating multidisciplinary pain centers as is now already routinely done. Relabelling is necessary by the hospital pharmacy since the lidocaine plasters are used off-label. All study drugs will need to be relabelled by the hospital pharmacies.

Patients who want to withdraw from the study medication will be offered an alternative according to standard clinical practice. This will imply that patients on the pregabalin arm will be offered an alternative systemic drug treatment (gabapentin) and patients on the topical arm will be offered a different topical drug (failing treatment with lidocaine medicated plasters will be treated with capsaicin patches and otherwise). Hence there will be no crossover from systemic to topical or vice versa, to preserve the comparison between the systemic versus topical treatment as much as possible during the trial.

5 STUDY SETTING

The study is conceived as a nation-wide multicenter study, involving at least 13 multidisciplinary pain centers (MPC) in Belgium. All the included pain centers are officially recognized by the Belgian health authorities (FOD) and have been shown to share the same experience in the diagnosis and treatment of neuropathic pain conditions. Especially, they share specialized competence in the diagnosis of localized neuropathic pain conditions following the recognized international guidelines.

Patients suffering from neuropathic pain conditions are found both in primary care as well as secondary care. This is due to the fact that neuropathic pain can result from all sorts of medical conditions, such as diabetes, surgery, trauma, entrapment syndromes, chemotherapy, HIV, radiation and so on. Such patients will therefore consult primary care physicians but will often also look for specialist care in later instance. Many of these patients will consult the pain centers for evaluation and treatment of these painful neuropathies. In addition, it should be stressed that all participating pain centers have intensive collaboration with primary care physicians so the referral of patients who are eligible for participation in this trial will cause no problems.

There are no different types of sites participating in this trial. All participating centers will screen and include patients and will take part in the follow-up of the treatment results. The participating physician-investigators in the different pain centers are specialists with each at least 5 years of experience in pain treatment. There will be no major differences between the centers participating in this trial since the requirements imposed on the centers are identical for all of them.

6 ELIGIBILITY CRITERIA

All patients suffering from **localized neuropathic pain syndromes (LNP)** are eligible for participation in the proposed trial. The definition of LNP was originally based on the International Association for the Study of Pain (IASP) definition of neuropathic pain, which is the most detailed that can currently be proposed: 'Localized neuropathic pain is a type of neuropathic pain that is characterized by consistent and circumscribed area(s) of maximum pain'. Pain which has distinct neuropathic features should be circumscribed to the same area or areas of maximal pain and sensory disturbances (see underneath for international definition). These skin areas are in accordance with underlying pathology and should be able to be covered by the maximum number of patches/plasters. Considering the area of the applied patches the maximum size of the painful skin area is limited to 520cm² (= 40 x 13cm).

This localized neuropathic pain (LNP) is often described by patients with symptoms such as shooting, burning, stabbing, or being like an electric shock. In addition, LNP can also show symptoms of irritable nociceptors, such as allodynia (mechanical) and hyperalgesia (cold). Allodynia is when a normally not painful stimulus – e.g. light touch or clothing running over the skin - becomes painful. If a minor/mild pain stimulus is causing severe pain it is called hyperalgesia.

Localized neuropathic pain is a type of neuropathic pain that is characterized by consistent and circumscribed area(s) of maximum pain, associated with positive sensory signs and/or spontaneous symptoms characteristic of neuropathic pain

All patients suffering from such neuropathic pain conditions can be screened for participation in this trial. The inclusion of patients will in no way be limited to certain etiologies such as post-herpetic neuralgia (PHN), diabetic polyneuropathy (DPN) or post-radiation neuropathies. In most commercial clinical neuropathic studies inclusion of patients will be limited to one single etiology (in most cases either PHN or DPN), and in addition many inclusion and exclusion criteria will be imposed. This is NOT the case in this pragmatic trial where all adult patients suffering from localized neuropathic pain (= clearly defined by the international definition) can be included in this study. There are no exclusions based on concomitant medication, such as analgesics or anti-depressants. These drug classes are also included in the calculation of the medication quantification score (MQS-III-R score).

Patients can use their own rescue mediation since all analgesic medications will be recorded through the MQS-III score (online registration).⁵⁴⁻⁵⁷ As such, the investigators will be able to evaluate and objectivize the intake of analgesic medication (lower intake of analgesics will result in lower MQS-III scores during the course of the trial). In addition, investigators will be able to closely monitor the need for analgesic rescue medication (to treat acute episodes of pain or exacerbations of chronic painful neuropathy in our case).

6.1 Inclusion criteria

Patients eligible for inclusion in this study must fulfil all of the following criteria:

- Subjects should be capable of giving their informed consent with sufficient knowledge of the Dutch, French or German language;
- Males and females, 18 years and older;
- Be assessed as suffering from moderate to severe neuropathic pain across the screening process with pain intensity (numeric rating scale – NRS) ≥ 4/10;
- At the time of screening pain symptoms have to be present for at least one (1) month, with a maximum of 24 months;
- Sensory disturbances present in the skin area of maximal pain;
- At the time of screening pain is clearly related to the presence of a localized neuropathic pain syndrome;
- Male or female patients of child producing potential* must agree to use contraception or take measures to avoid pregnancy during the study and until after the final treatment;
- Women can only be included after negative pregnancy test;

For female patients: Women of childbearing potential* must be willing and able to use an acceptable effective contraception until treatment discontinuation.

For male patients: Men who are fertile** with partners of childbearing potential must be willing to use an acceptable effective contraception until treatment discontinuation.

*A women is considered of childbearing potential (WOCBP), i.e. fertile, following menarche and until becoming post-menopausal unless permanently sterile. Permanent sterilisation methods include hysterectomy, bilateral salpingectomy and bilateral oophorectomy. A postmenopausal state is defined as no menses for 12 months without an alternative medical cause.

**A man is considered fertile after puberty unless permanently sterile by bilateral orchidectomy.

Birth control methods which may be considered effective when used consistently and correctly:

- Combined (estrogen and progestogen containing) hormonal contraception associated with inhibition of ovulation:
 - Oral
 - Intravaginal
 - Transdermal
- Progestogen-only hormonal contraception associated with inhibition of ovulation:
 - Oral

- Injectable
- Implantable
- Progestogen-only oral hormonal contraception, where inhibition of ovulation is not the primary mode of action
- Intrauterine device
- Intrauterine hormone-releasing system
- Male or female condom with or without spermicide
- Cap, diaphragm or sponge with spermicide
- Bilateral tubal occlusion
- Vasectomised partner
- Sexual abstinence

List of contraception methods meeting the criteria is also provided in the patient information.

6.2 Exclusion criteria

- Age < 18;
- Pregnant and breastfeeding women;
- Infection in the painful skin region;
- Poorly healed or non-healed wound or scar in the painful skin region as well as presence of cutaneous abnormalities (non-intact skin barrier) within the painful skin region related to dermatological conditions;
- Known and/or strong suspicion of allergy to the study medication, known skin disorder (resulting in disruption of the normal skin barrier);
- Previous treatment with any of the three medications included in the study protocol for the same painful area within the last 12 months at the time of screening;
- Risk of heart failure and/or renal failure.

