8.6 Dosage schedules

The following dosage schedules will be applied during the study. It should be stressed that all doses concern adult dosing, since no infants or children will be included in this study.

- (1) **Pregabalin** (oral route of administration) generics providing pregabalin 75mg capsules in packages containing 200 capsules
 - a. Should be swallowed two times a day (morning and evening).
 Administration of pregabalin with food has no clinically significant effect on the extent of pregabalin absorption.

- b. Pregabalin treatment should be started with a dose of 150mg per day given as two divided doses (2 x 75mg per day). Based on individual patient response and tolerability, the dose may be increased to 225mg per day after an interval of 3 days, and if needed, then to a daily dose of 300mg after an additional 3-days interval. Or can be decide otherwise if in accordance with current clinical practice or patient-specific conditions requiring changes to the dosing schedule.
- c. Pregabalin treatment can be further increased to a maximum dose of 600mg per day through dosage increases of 75mg every 72 hours.
- d. In case of vomiting after intake of pregabalin, no additional intake is necessary and regular dosing schedule will be maintained.
- e. In accordance with current clinical practice, if pregabalin has to be discontinued, it is recommended this should be done gradually over a minimum of 1 week.
- f. In patients with mild or moderate renal impairment a dosage adjustment is not required. If creatinine clearance is < 30 ml/min, a dose adjustment is required per protocol.

Renal impairment: pharmacokinetics

Pregabalin clearance is directly proportional to creatinine clearance. In addition, pregabalin is effectively removed from plasma by haemodialysis (following a 4 hour haemodialysis treatment plasma pregabalin concentrations are reduced by approximately (50%). Because renal elimination is the major elimination pathway, dose reduction in patients with renal impairment and dose supplementation following haemodialysis is necessary.

- g. No dose adjustment is required for patients with hepatic repairment.
- h. Patients should take a missed dose as soon as possible, except when it is time for the next dose. It is important not to take a double dose.

(2) **Lidocaine 5% medicated plaster** (topical administration) – Versatis

- a. One daily application during 12 consecutive hours within a 24 hours period.

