- b. Each plaster must be worn no longer than 12 hours. The subsequent plaster-free interval must be at least 12 hours. The plaster can be applied during the day or during the night. If patients forget to remove the plaster after 12 hours, the plaster should be removed as soon as noticed.
- c. Maximum of 3 plasters during the same application.
- d. In patients with mild or moderate renal impairment a dosage adjustment is not required. If creatinine clearance is < 30 ml/min, a dose adjustment is required per protocol (max daily dose 1.5 patch).
- e. In patients with mild or moderate hepatic impairment a dosage adjustment is not required. In patient with severe hepatic impairment, the plaster should be used with caution.

- f. The plaster should not be applied to mucous membranes. Eye contact with the plaster should be avoided.
- g. The plaster may only be placed on dry, intact, skin.

(3) Capsaicin 8% patch (topical administration) - Qutenza

- a. Treatments with the capsaicin 8% patch may be repeated every 90 days, as warranted by the persistence or return of pain.
- b. Patch should be applied to the most painful skin area. Maximum number of patches is equal to the number needed to cover the painful area. The surface of this area cannot be larger than 520cm2.
- c. No dose adjustment is required for patients with renal or hepatic impairment.
- d. Patches should not be held near eyes or mucous membranes.
- e. Qutenza must be applied to intact, non-irritated, dry skin and allowed to remain in place for 30 minutes on the feet, and 60 minutes for all other locations.

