8.7 Dosage modifications

Dosage of pregabalin is changed every 3 days. Starting dose will be 150mg per day (75mg in the morning and 75mg in the evening). Based on individual response and tolerability, the dose of pregabalin may be further increased to 225mg after an interval of 3 days, and to 300mg after an additional 3-day interval. Dosage can be further increased to the maximum daily dose of 600mg through dosage increases of 75mg every 3 days. Or can be decide otherwise if in accordance with current clinical practice or patient-specific conditions requiring changes to the dosing schedule.

- The dosage of pregabalin can always be modified upon request by the patient. Reasons to modify the dosage could be occurrence of side effects after increase of daily dose (in most cases dizziness, sedation, peripheral edema, blurred vision or nausea and vomiting). In case of side effects, the daily dose should be reduced in first instance by 75mg. If side effects persist additional reductions in daily dose by 75mg should be performed until side effects have (almost) disappeared. All the dose changes (increase and decrease) should be captured in the patient file and the eCRF. If decrease of the dosage appears, also the reason (side effect) will be documented.
- Adjustment of dosage can be done at home following medical guidance.
- Standard of care will be applied to treat side effects.
- Intake of medication can at any time be stopped by the patient if the patient suffers from in his/her opinion unacceptable side effects (no need for tapering down the medication dose).

If systemic treatment is stopped by the patient or the treating physician due to side effects then there is a possibility to switch to another systemic anti-neuropathic treatment, gabapentin. Starting daily dose is 600mg (300mg x 2), to be increased by 300mg every three days to a maximum daily dose of 1800mg (dose including down titration can always be modified by the patient). Or can be decide otherwise if in accordance with current

clinical practice or patient-specific conditions requiring changes to the dosing schedule. Gabapentin is provided by the hospital pharmacy in a dose of 300mg preferably in a package containing 200 capsules. All the dose changes (increase and decrease) should be captured in the patient file and the eCRF. If decrease of the dosage appears, also the reason (side effect) will be documented.

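### The renal dosing rules in 8.6 have no scheduled creatinine clearance to trigger them, and the pregabalin text gives no adjusted dose and is inconsistent on mild or moderate impairment

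*Protocol*

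**What the plan says.** Section 6.2 excludes patients with "Risk of heart failure and/or renal failure" and gives no laboratory limit.

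Section 8.6 sets renal dosing rules for the three products:

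- **Pregabalin, item f.** "In patients with mild or moderate renal impairment a dosage adjustment is not required". Then: "If creatinine clearance is < 30 ml/min, a dose adjustment is required per protocol". No adjusted dose follows, there or in 8.7.
- **Pregabalin, pharmacokinetics paragraph directly after item f.** "Pregabalin clearance is directly proportional to creatinine clearance", and "Because renal elimination is the major elimination pathway, dose reduction in patients with renal impairment and dose supplementation following haemodialysis is necessary".
- **Lidocaine, item d.** The same threshold, this time with a dose: "If creatinine clearance is < 30 ml/min, a dose adjustment is required per protocol (max daily dose 1.5 patch".
- **Capsaicin, item c.** No renal adjustment.

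Screening (7.1.2 and the screening column of 7.8) consists of consent, the eligibility check, demographics, medical and surgical history, alcohol frequency, sensory testing and a pregnancy test. The clinic visits (7.7, 7.8) cover the study intervention, size of the painful area, adverse events, systemic side effects, concomitant medication and, at V2 and V4, sensory testing.

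**The concern.** A dose rule with a numeric trigger works only if someone has the number. Here the trigger is a creatinine clearance that the protocol never asks a site to obtain or look up. The exclusion could act as a first filter, but it rests on the site's view of who is at risk, and the value that would inform that view is not collected either.

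Section 7.1.1 recruits patients on their first visit to a pain centre and by direct referral from general practice, so a recent renal value need not be on file at the site. How risk of renal failure is read may also differ among the 13 or more centres.

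The pregabalin text adds a second problem. A site that does know a patient's clearance is told to adjust per protocol, but the protocol prints no dose. A site with a patient in mild or moderate impairment reads that no adjustment is needed, and a few lines later that reduction in renal impairment is necessary.

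Patient safety and uniform dosing are at stake in two of the three arms.

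**Working it through.** The protocol gives no figure to reproduce. The check sets its sections side by side; three short calculations give scale.

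**1. Is the trigger collected?** Clinic time points in 7.8: screening plus V1 to V6 = 1 + 6 = 7. Time points with creatinine, eGFR or clearance: 0. The online assessments in 7.7 are questionnaires. Creatinine as a test appears only in the general-practice screening tool (Appendix 5), as one of several aetiological tests to consider. The mentions of laboratory data in 11.1 and of laboratory abnormalities in Appendix 2 are generic and schedule nothing. By contrast, the pregnancy exclusion is backed by a scheduled test.

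**2. Does the exclusion make the dose rule redundant?** No. Section 8.6 itself provides for clearance below 30 ml/min and mentions haemodialysis, so it foresees such patients on treatment.

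**3. Does the adjustment lead to a dose?** For lidocaine it does: 1.5 patches a day against the general maximum of 3, so a patient below the threshold who is not recognised could use 3 / 1.5 = 2 times the permitted amount. For pregabalin it does not, and the ordinary ceiling remains: "Dosage can be further increased to the maximum daily dose of 600mg through dosage increases of 75mg every 3 days".

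**4. Do the two pregabalin statements agree?** Item f limits adjustment to clearance below 30 ml/min. The next paragraph requires reduction in renal impairment and sets no limit. Its stated reason, clearance proportional to creatinine clearance, applies at every degree of impairment. As written they do not agree.

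**5. What does the proportionality imply?** Exposure at a fixed dose = dose / clearance. With pregabalin clearance proportional to creatinine clearance, the exposure ratio = reference clearance / patient clearance. The protocol gives no normal value, so I assume 90 ml/min, with a range of 80 to 120.

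| Patient clearance | Reference 80 | Reference 90 | Reference 120 |
|---|---|---|---|
| 60 ml/min | 80/60 = 1.3 | 90/60 = 1.5 | 120/60 = 2.0 |
| 30 ml/min | 80/30 = 2.7 | 90/30 = 3.0 | 120/30 = 4.0 |

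Neither 60 nor 30 ml/min is below 30, so item f requires no adjustment at either. These ratios hold only at a fixed dose. Because pregabalin is titrated to tolerability, they illustrate the text's own premise and do not forecast exposure in the trial.

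**The case against.** The case against is substantial on consequences.

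- **Titration is not blind.** Under 8.6 and 8.7 each increase depends on response and tolerability. Side effects call for 75 mg reductions, repeated until they have almost disappeared. Side effects are reported online every week (7.7), and treatment, dosage and compliance are reported weekly as well (8.8).
- **Sites have room to act.** History is taken at screening, and 8.6 adds: "Or can be decide otherwise if in accordance with current clinical practice or patient-specific conditions requiring changes to the dosing schedule".
- **The label stands behind the protocol.** Section 8.3 says the SmPC is used. Section 2.1 says the products are used within their marketing authorisation, apart from lidocaine's indication. The missing pregabalin dose is therefore close to a missing cross-reference.
- **The exclusion is cautious.** Risk of renal failure is wider than established failure. Specialists apply it and monitors verify eligibility (section 12).
- **The pharmacokinetics paragraph may only explain item f.** It has its own heading and follows directly on the threshold of 30 ml/min.

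Most of this stands as mitigation. None of it supplies the missing value: history and patient-specific dosing need the impairment to be known, and side-effect rules act after exposure. The last reading is possible, but the paragraph does not say it.

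Three stronger readings are tempting and are not supported:

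- A reader might infer that pregabalin runs unchecked to 600 mg a day before the first post-baseline visit. The fastest schedule does get there by day 18 ((600 − 150) / 75 = 6 steps of 3 days), but that is the fastest permitted path and each step is conditional. V2 has no renal test either, so the timing of that visit adds nothing.
- A reader might infer that sites receive flatly contrary orders. The explanatory reading of the second paragraph rules that out; what remains is an unresolved inconsistency.
- A reader might infer a measurable bias against pregabalin in the EQ-5D-5L comparison. The protocol gives no prevalence of renal impairment, so no size can be put on it.

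**Conclusion.** The point holds in two parts.

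**Wrong as written:** the pregabalin text in 8.6. Item f and the paragraph after it are inconsistent on mild or moderate impairment, and the adjustment below 30 ml/min has no dose attached.

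**A cheap improvement:** the missing renal value. The rule for pregabalin and lidocaine has no collected trigger at any of the 7 time points, so unrecognised severe impairment passes both 6.2 and 8.6. Existing safeguards lower the risk but do not close that gap.

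The number of patients affected is unknown and I do not estimate it. The exposure ratios rest on an assumed normal clearance and a fixed dose; the verdict does not depend on them. Capsaicin dosing, the sample size and the type I error are not affected. The change should be made on grounds of safety and uniform dosing.

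**What to change.** 1. **7.1.2 and the screening column of 7.8:** record the most recent creatinine clearance from the medical record before randomisation, with a maximum age chosen by the sponsor. Ask for a routine creatinine only where no recent value is on file.
2. **8.6, pregabalin:** refer renal dosing explicitly to the SmPC named in 8.3, or state the dose by clearance band. Reword item f and the pharmacokinetics paragraph so that they say the same about mild and moderate impairment.
3. **6.2:** if a numeric renal threshold is added, add it as a minimum alongside the present wording. Replacing that wording with the only figure in 8.6, 30 ml/min, would admit patients whom an investigator may now exclude. Neither the renal nor the heart-failure exclusion should become narrower.

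Cost: amendment wording, one eCRF field, an occasional routine creatinine and a few more screen failures. A screening value will not detect later decline, which still depends on routine care.
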